1.4.3 Discussion

Considering this patient population, and the need to adequately monitor suicidality, frequent clinic and phone visits, which include C-SSRS assessments, are planned in this trial to monitor patients.

Additionally, all patients will be allowed to continue antidepressants and other psychiatric medications (i.e. non-benzodiazepine anxiolytics) if on stable treatment at the time of trial entry and throughout the whole trial performance. Considering the mechanism of action of BI 1358894 and the adverse events reported in clinical trials to date, there is no undue risk related to stopping the trial drug during the treatment period or at the end of the treatment period, nor any major risk related to potential aggravation of the side effect profile/s of the background medication/s.

After patients have completed trial participation, they should return to treatment as prescribed by their treating physicians.

Embryo-fetal development toxicity has been identified in a pre-clinical study in minipigs at relevant human exposure levels. Therefore, a risk for teratogenicity in humans cannot be excluded. It is of high importance that WOCBP strictly adhere to contraceptive measures consisting of one highly effective method of birth control per ICH M3 (R2) that results in a low failure rate of less than 1% plus one additional barrier method during the treatment and follow-up period of the study. Sexual abstinence as a contraceptive method will not be allowed for WOCBP who are heterosexually active. Pregnancy testing has to be performed at every site visit. Additionally, WOCBP will be repeatedly counselled with regard to the need for contraception at all visits as per Flow Chart 1 (including phone visits).

Considering the acceptable and manageable safety profile of BI 1358894 as demonstrated in nonclinical and toxicology studies, good tolerability in clinical studies performed to date, close monitoring (including the above-mentioned risk mitigation activities to minimize the risk of pregnancy during the trial) planned during the trial visits and the involvement of an independent external DMC, the potential risks to the patients will be minimized and outweighed by a potential therapeutic benefit of the trial drug and more effective treatment for patients with PTSD.

Page 41 of 148

Proprietary confidential information © 2023 Boehringer Ingelheim International GmbH or one or more of its affiliated companies

2. TRIAL OBJECTIVES AND ENDPOINTS

2.1 MAIN OBJECTIVES, PRIMARY AND SECONDARY ENDPOINTS

2.1.1 Main objectives

The main objective of this trial is to provide proof of concept (PoC) of orally administered BI 1358894 125mg after eight weeks treatment in patients with PTSD compared to placebo.

2.1.2 Primary endpoint(s)

Change from baseline in Clinician-Administered PTSD Scale for DSM-5 (CAPS-5) total severity score at Week 8

2.1.3 Secondary endpoint(s)

CAPS-5

- Response defined as ≥30% CAPS-5 reduction from baseline at Week 8
- Response defined as ≥50% CAPS-5 reduction from baseline at Week 8

PCL-5

- Change from baseline on the PTSD Checklist for DSM-5 total score at Week 8

Page 42 of 148

Proprietary confidential information © 2023 Boehringer Ingelheim International GmbH or one or more of its affiliated companies

2.2.3 Safety

Safety will be assessed descriptively in patients who received at least one dose of study drug, including:

[figure not shown]
- Percentage of patients with (S)AEs (including clinically relevant abnormalities of physical examination, vital signs, ECG test and laboratory tests)
- Suicidality as assessed by C-SSRS
- Occurrence of protocol-specified adverse events of special interest (AESI)

Proprietary confidential information © 2023 Boehringer Ingelheim International GmbH or one or more of its affiliated companies

3. DESCRIPTION OF DESIGN AND TRIAL POPULATION

3.1 OVERALL TRIAL DESIGN

This is a Phase II, 8-week-treatment, multicenter, randomized, double blind, placebo-controlled, parallel-group trial in patients with Post-Traumatic Stress Disorder (PTSD). In total, approximately 286 male and female patients with PTSD meeting the entry criteria are planned to be randomized into this trial.

V = Visit, W = Week, EOT = End of Treatment, EOS = End of study, ☎ = Telephonic Visit

Figure 3.1: 1 Trial design

Patients are enrolled into the trial after informed written consent has been obtained. Eligible patients will be randomized to double-blind treatment with either placebo (approx. n=143) or BI 1358894 at 125 mg QD (approx. n=143). Total treatment duration will be eight weeks, refer to Figure 3.1: 1.

After the completion of the 8-week double-blind treatment period or following early discontinuation of the trial at any timepoint, patients will complete the 4-week follow-up period with the end of study (EOS) visit. All (S)AEs, including those persisting after individual patient's end of study must be followed up until they have resolved, have been assessed as "chronic" or "stable", or no further information can be obtained. Individual patient participation is concluded when the patient has completed their last planned visit (end of study visit) (refer to sections 3.3.4.1 and 3.3.4.2).

An interim analysis is planned when the 120th evaluable patient completes the Week 8 visit. The purpose of this interim analysis is for internal planning of the PTSD indication with BI 1358894. Please refer to section 7.2.8

Page 44 of 148

Proprietary confidential information © 2023 Boehringer Ingelheim International GmbH or one or more of its affiliated companies

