3.3.4.1 Discontinuation of trial treatment

Ideally, the patient should attend all remaining visits and perform all study related procedures according to Flow Chart 1, Flow Chart 2 and section 6.2.2 An early EoT (eEOT) Visit shall be conducted within 7 days of the last dose of trial medication for patients who agree to conduct regularly scheduled visits after premature drug discontinuation (if consistent with the planned visit schedule, the eEOT can replace the next regularly scheduled clinic visit). After this early EOT visit, patients should be followed up according to the regularly scheduled visit for both clinic and phone visits including Visit 10 and should be encouraged to complete the EOS Visit 28+2 days after the drug discontinuation date. All procedures should be completed, with the exception of trial drug procedures and PK collections. If a regular planned visit is completed prior to the initially planned Visit10 (early drug discontinuation date + 28+2 days), no additional FUP Visit may be needed. However, end of study participation (EOS) must be completed.

If the patient does not agree to return for all remaining scheduled visits, the patient should be encouraged to return at least for an early EoT (eEOT) Visit within 7 days of the last dose of trial medication, for the regularly scheduled Visit 10 and EOS. If EOS visit (early drug discontinuation date + 28 +2 days) can be completed prior to the date of the planned Visit 10, no additional FUP Visit may be needed. However, end of study participation (EOS) must be completed.

Should the patient not agree to any further clinic visits, at least phone contacts should occur at the scheduled visit time points, should that not be acceptable, a phone contact at the end of the planned observation period (i.e. 12 weeks after start of treatment or 4 weeks after last dose) should occur to collect the most relevant information: vital status (please see section 5.4.6.2.1) adverse events, or last contact date in case of lost to follow-up.

Patients who refuse all of the above are considered to have fully withdrawn consent to participate in the trial. In this case, the patient does not need to justify the decision and should be withdrawn from the trial and all follow-up assessments (please refer to section 3.3.4.2).

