5.4.6.2 Adverse event collection and reporting

5.4.6.2.1 AE Collection

The investigator shall maintain and keep detailed records of all AEs in the patient files. The following must be collected and documented on the appropriate CRF(s) by the investigator:

- From signing the informed consent onwards until the individual patient's end of trial (= the End of Study (EoS) visit): all AEs (serious and non-serious) and all AESIs.
- After the individual patient's end of trial: the investigator does not need to actively monitor the patient for new AEs but should only report any occurrence of cancer and trial drug related SAEs and trial drug related AESIs of which the investigator may become aware of by any means of communication, e.g. phone call. Those AEs should be reported on the BI SAE form (see section 5.4.6.2.2), but not on the CRF.

Vital Status Data Collection

Patients who discontinue trial treatment prematurely, who agree to be contacted further but do not agree to physical visits, should be followed up as described in section 3.3.4.1, withdrawal from trial treatment. From then on until the individual patient's end of the trial the investigator must any occurrence of cancer, report all deaths / fatal AEs regardless of

Page 79 of 148

Proprietary confidential information © 2023 Boehringer Ingelheim International GmbH or one or more of its affiliated companies

relationship, and trial drug related SAEs and trial drug related AESIs the investigator becomes aware of.

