Randomization should not be performed in case of a positive urine pregnancy test (to be completed locally on-site using kits provided by central lab). In this case, a serum pregnancy test will be performed by the central lab for confirmation.

Upon randomization via the IRT, medication kit will be dispensed. Trial medication is
administered after
The first dose should be taken at the clinic after all Visit 2 assessments and procedures are
completed, except for remaining patient reported clinical outcome assessments including
optional speech recordings as described above, and followed by

. Samples for optional plasma/serum and DNA biobanking will be collected if Informed Consent is provided. A sample for DNA biobanking is preferentially collected at Visit 2 but can be collected at another time point thereafter.

Trial drug kits will be dispensed for home administration.

Visit 4, Visit 6, Visit 8

Patients should not take trial medication before coming to the clinic. This is because patients will be dosed at the clinic. When applicable, dosing should occur after safety lab samples and samples are taken if applicable (please refer to Appendix 10.2).

Pandemic restrictions

At Visit 6, the patient will be presented with questions to evaluate the impact of COVID-19 pandemic restrictions. The assessment period will be aligned with the CAPS-5 recall period (i.e. past week).

Phone visits

Visit 3, Visit 5, Visit 7 and Visit 9 will be conducted by phone or by video call, if in line with local regulation.

At Visit 9, patients will be instructed to take the last dose of study medication on **the day before** the EOT visit.

Page 93 of 148

Proprietary confidential information © 2023 Boehringer Ingelheim International GmbH or one or more of its affiliated companies

Visit 10 / End of Treatment (EOT) Visit

For patients completing the 8-week treatment, this visit will be EOT visit. For patients who discontinue study treatment prematurely and continue with study visits, this visit at Week 8 will be their Visit 10.

EOT visit represents the end of the treatment period. Last study drug administration will be on the day before EOT visit. The overall duration of the anticipated treatment period (Randomization to EOT) should not be less than 56 days; therefore the EOT visit is scheduled at Day 57 with a visit window of up to +2 days.

Patients prematurely discontinuing study drug

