6.2.3 Follow-up period and trial completion

For all patients who had at least one dose of trial medication, the follow-up visit will be performed as described in section 3.3.4.1 and 3.3.4.2.

If the last day of trial drug intake is different from the day prior to the EOT visit, the date of the last day of trial drug intake will be used for calculation of the FUP/EOS visit date.

Patients who finish the randomized treatment period according to the protocol, will return to the clinic for the end of study (EOS) Visit 11. Trial completion is defined as patients having reached the EOS visit within the specified window per the Flow Chart 1. The trial completion page in the eCRF has to be entered.

For all randomized patients, termination of trial medication and trial completion must be recorded on the corresponding eCRFs.

Should it be not possible for the patient to attend a follow up visit at the trial site, a visit out of time window should be performed as soon as possible; if a visit at the site is not possible at all, at least a phone contact should occur at the scheduled follow-up visit time point (please refer to section 3.3.4.1 and 5.4.6.2.1).

Page 94 of 148

Proprietary confidential information © 2023 Boehringer Ingelheim International GmbH or one or more of its affiliated companies

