7.2.2 Handling of Intercurrent Events

In the analyses of the primary endpoint, the following intercurrent events (ICEs) are of interest:

- 1. Change in background CNS active medication (e.g., non-SSRI antidepressant, anxiolytics)
- 2. Change in pharmacological therapy (SSRI)
- 3. Change in drug test result from negative to positive (Cannabis, Benzodiazepine, Barbiturates, Opiates, Cocaine, Amphetamines, Methadone, PCP)
- 4. Change in non-pharmacological therapy trauma-focused psychotherapy

Proprietary confidential information © 2023 Boehringer Ingelheim International GmbH or one or more of its affiliated companies

- 5. Change in non-pharmacological therapy all other cognitive/behavioral therapy (CBT) (e.g., any other kind of psychotherapy, nicotine withdrawal therapy, diet, etc.)
- 6. Withdrawal of study medication due to investigator assessed drug-related adverse events (e.g., headache)
- 7. Withdrawal of study medication due to perceived lack of efficacy or disease worsening
- 8. Withdrawal of study medication due to other adverse events
- 9. Withdrawal of study medication due to any other reasons

Table 7.2.2:1 Handling rules for Intercurrent events

	ICE	Primary Estimand	Supplementary Estimand
Handling rules for ICEs	1-4	Treatment policy	Treatment policy
	5	Treatment policy	Treatment policy
	6-7	Hypothetical	Treatment policy
	8-9	Hypothetical	Hypothetical

The primary estimand estimates the treatment effect when changes to background CNS active medication, pharmacological SSRI therapies and non-pharmacological therapies (ICEs 1-5) are considered to be part of the treatment effect, but changes to randomized treatment (ICEs 6-9) are not considered to be part of the treatment effect of interest. ICEs are therefore handled by a hybrid estimand that combines the treatment policy and hypothetical approaches, where ICEs 1-5 are handled using the treatment policy approach, and measurements taken after the occurrences of these ICEs are included in the primary analysis; ICEs 6-9 are handled using the hypothetical approach, and measurements after their occurrences are therefore censored in the primary analysis.

Page 96 of 148

Proprietary confidential information © 2023 Boehringer Ingelheim International GmbH or one or more of its affiliated companies

Regardless of the occurrence of ICEs, every attempt will be made to follow all patients until the end of the planned study period.

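### For patients who stop drug by Day 28 and stay in follow-up, EOS marks the end of the trial and of AE collection, yet it falls before a Visit 10 that the plan still schedules

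*Protocol*

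**What the plan says.** **EOS as the end of the trial.** Protocol 3.1: "Individual patient participation is concluded when the patient has completed their last planned visit (end of study visit"; the sentence then refers to 3.3.4.1 and 3.3.4.2. Flow Chart 1 marks completion of participation only at Visit 11, and its footnote 14 equates the EOS visit with the individual patient's end of trial. Section 5.4.6.2.1 sets the AE collection period: "From signing the informed consent onwards until the individual patient's end of trial (= the End of Study (EoS) visit): all AEs". After that point "the investigator does not need to actively monitor the patient for new AEs", and only cancers and drug-related SAEs and AESIs that come to the investigator's attention are reported. Section 6.2.3 adds: "Trial completion is defined as patients having reached the EOS visit within the specified window per the" flow chart.

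**EOS as a visit timed from the drug stop.** Section 3.3.4.1 says that early discontinuers "should be encouraged to complete the EOS Visit 28+2 days after the drug discontinuation date". It foresees that this can come first: "If EOS visit (early drug discontinuation date + 28 +2 days) can be completed prior to the date of the planned Visit 10", an extra FUP visit may not be needed, but EOS must still be completed.

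**Visit 10 still planned.** Section 3.3.4.1 asks early discontinuers to attend the remaining visits including Visit 10, and asks those who decline the full schedule to come at least for eEOT, Visit 10 and EOS. Section 6.2.2 treats their Week 8 visit as Visit 10. Flow Chart 1 has AE assessment at Visit 10. Flow Chart 2 has CAPS-5, PCL-5 and C-SSRS there, but no CAPS-5 or PCL-5 at Visit 11. Section 5.4.5.1 requires C-SSRS ideation of type 4 or 5, and any suicidal behaviour, to be reported as SAEs throughout trial participation. SAP Table 6.1:2 runs the follow-up phase to the last protocol visit.

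**The concern.** One label does two jobs. As a safety visit, EOS is tied to the patient's own last dose. As an administrative milestone, it closes participation and active AE collection. For completers the two coincide, because EOS is the last visit. For a patient who stops early and stays in follow-up, EOS can come first, with Visit 10 after it.

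Two things are at stake. The first is safety reporting between EOS and Visit 10. Section 5.4.6.2.1 narrows it to cancer and drug-related SAEs and AESIs, while the flow charts, 5.4.5.1 and the SAP treat the patient as still in the trial. The second is the Week 8 CAPS-5 and PCL-5. A site that reads EOS as the end of the trial could close the patient without them. The supplementary estimand handles by treatment policy both drug-related AE withdrawals (intercurrent event 6) and intercurrent event 7, "Withdrawal of study medication due to perceived lack of efficacy or disease worsening". For those patients it uses the value after stopping.

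**Working it through.** **Inputs.** Let d be the day of last dose, with first intake on Day 1.
- EOS for early discontinuers: Day d+28 to d+30 (protocol 3.3.4.1; 6.2.3 dates it from the last intake).
- Visit 10: Day 57 to 59 (6.2.2: "therefore the EOT visit is scheduled at Day 57 with a visit window of up to +2 days").
- Residual effect period for safety: 28 days (protocol 7.2.6, SAP 6.1).

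**Plan's own figure.** For completers, EOS is Day 57 + 28 = Day 85, and (85 − 1)/7 = 12. This is Week 12, as Flow Chart 1 states. Visit 10: (57 − 1)/7 = 8, also as stated.

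**Order of visits.**
- Nominal EOS before Visit 10: d + 28 < 57, so d ≤ 28.
- Whole EOS window before Visit 10: d + 30 < 57, so d ≤ 26.
- Nominal gap: 57 − (d + 28) = 29 − d days.

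| Last dose (day) | EOS window | Visit 10 window | Nominal gap |
|---|---|---|---|
| 1 | 29-31 | 57-59 | 28 days |
| 14 | 42-44 | 57-59 | 15 days |
| 26 | 54-56 | 57-59 | 3 days |
| 27 | 55-57 | 57-59 | 2 days, windows touch |
| 28 | 56-58 | 57-59 | 1 day, windows overlap |
| 29 | 57-59 | 57-59 | none |

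**Which AEs fall in the gap.** The treatment-emergent period ends at d+28, so events after EOS are not treatment-emergent and the main AE tables are untouched. SAP 7.8.1 assigns events in the 28 days after the residual effect period, Day d+29 to d+56, to follow-up and tabulates them. Since 57 ≤ d + 56 for every d ≥ 1, the nominal gap lies within that interval. The follow-up AE table therefore covers days on which 5.4.6.2.1, read literally, has ended active collection.

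**Which efficacy analyses use the value.** Protocol 7.2.2 and SAP 6.3 treat intercurrent events 6-9 as hypothetical in the primary estimand and censor data after the drug stop, so Visit 10 of these patients does not enter. In the supplementary estimand, events 6-7 are treatment policy and use it; events 8-9 remain hypothetical.

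**Related SAP check.** In SAP Table 6.7:1 the Visit 10/EOT window runs from Day 53 to d+7. For d ≤ 28 the upper end is at most Day 35, so the window is empty. Day 57 lies in the End of Trial window (d+8 to d+30) for d = 27 or 28 and in neither window for d ≤ 26. Placing these values at Week 8 rests on the general sentence in the eEOT row that maps efficacy data collected after stopping to later visits.

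**The case against.** The strongest reply is that the protocol keeps these patients in the trial. Section 3.1 ends participation at the last planned visit and points to 3.3.4.1, which plans Visit 10 for them. The overlap is foreseen: what 3.3.4.1 waives is an extra FUP visit, never Visit 10, and it separates holding that visit from completing EOS. Sections 7.2.2 and 7.3 call for every effort to follow patients and collect complete data. AEs and C-SSRS are assessed at Visit 10.

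Most of this stands. A reader might infer that the Week 8 CAPS-5 lies after the patient has left the trial, and the documents do not support that. A reader might also infer that the supplementary analysis collapses into the primary one. The public text does not show how that estimand is estimated, so this cannot be checked.

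A count is tempting too: 30% of 286 is 85.8, and half of that is about 43. But the 30% in protocol 7.5 is a study drop-out rate. Study drop-outs lack Week 8 data however EOS is defined. The group at issue is patients who stop drug and remain in follow-up, for whom no number is given.

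The trial-completion wording in 6.2.3 follows a sentence about patients who finish treatment, medication termination is recorded separately, and no visible analysis set uses completion. It has no shown analytic effect.

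What the reply does not remove is footnote 14 and 5.4.6.2.1, which equate the EOS visit with the patient's end of trial without exception. They cannot both hold with AE and C-SSRS assessment and SAE reporting at a later Visit 10.

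**Conclusion.** The point holds as a contradiction to reconcile. With a last dose by Day 28 (by Day 26 across the whole visit window), the EOS visit precedes Visit 10 by a nominal 1 to 28 days. In that interval the AE and SAE reporting rules conflict: 5.4.6.2.1 narrows them, while Flow Charts 1 and 2, 5.4.5.1 and the SAP follow-up phase do not. Treatment-emergent AE tables are unaffected; follow-up AE data and non-drug-related SAEs are exposed.

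For efficacy, the Week 8 CAPS-5 and PCL-5 are scheduled and the primary estimand is untouched. The remaining risk is that a site closes a patient at EOS and loses a value that matters only for intercurrent events 6-7 in the supplementary estimand. How many patients this concerns cannot be derived from the documents. The conclusion assumes that the discontinuation date is the last-dose date, as 6.2.3 indicates, and that the patient agrees to stay in follow-up.

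**What to change.** Separate the 28 (+2)-day safety follow-up from the end of participation, and reconcile protocol 3.1, 3.3.4.1, 5.4.6.2.1, 6.2.3 and Flow Chart 1 (completion row, double-asterisk footnote and footnote 14). One rule suffices: for early discontinuers who agree to follow-up, participation and AE collection end at the later of Visit 10 and the 28 (+2)-day follow-up, and completing that follow-up early does not replace Visit 10 with its CAPS-5 and PCL-5. In SAP Table 6.7:1, say explicitly that efficacy data collected around Day 57 after an early stop are assigned to Visit 10 for estimands that use them.

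The cost is wording. Visit 10 is already requested, so no visit or procedure is added. The downside is that, compared with a literal reading of 5.4.6.2.1, active AE recording runs up to about 4 weeks longer for these patients.
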